NKTR-118 was well-tolerated in the Phase II study at 5 and 25 mg/day with the most commonly reported side effects being GI in nature (abdominal pain, diarrhea, and nausea) and most frequent in the 50 mg cohort. The frequency of any GI AE was 53% in the 25 mg/day dose group and 48% in the corresponding placebo group. In the 50 mg/day dose group, the GI AE frequency was 69% and 27% in the corresponding placebo group. In the 5 mg/day dose group, the frequency was 46% and 34% in the corresponding placebo group. Most of the AEs were rated mild or moderate. During the double-blind phase, a total of 12 patients discontinued the treatment permanently due to AEs (10 patients in the 50 mg dose group, 1 patient in the 25 mg/day dose group, and 1 patient in the 5 mg/day dose group). Most of the discontinuations were due to GI AEs. There was 1 serious adverse event (SAE) of upper abdominal pain in the 50 mg dose cohort, which was considered to be related to the study drug by the investigator. The patient was briefly monitored in a hospital setting due to this event, which resolved spontaneously without medical sequelae. No reversal of analgesia was seen at any dose in Phase II, as measured by changes in the daily opioid dose or by Numerical Rating Scale (NRS) for pain. A significant increase in total Clinical Opioid Withdrawal Scale (COWS) score for the NKTR-118 50 mg group was noted as compared with placebo at Day 1 of the double-blind treatment period. When the GI component of the COWS instrument (eg, diarrhea, abdominal cramps) was removed from calculation of total COWS scores, there was no longer a significant difference, indicating a lack of increase in the components of the scale that reflect CNS withdrawal. Although these data suggest that the risk for reversal of analgesia or precipitation of opioid withdrawal is unlikely, it is recommended that investigators remain vigilant regarding this potential effect of NKTR-118.

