Patients enrolled in this study may not experience any benefit from being in the study regardless of the treatment arm that they are randomized to. For patients assigned to the NKTR-118 arm, a rescue medication is incorporated in the study design by use of bisacodyl if no SBM has occurred within at least 72 hours since the previous one. Further guidance is provided on the use of bisacodyl and an enema. For patients in the Usual Care group, care of OIC will be managed by the investigator.

The Usual Care arm is included in this study to allow for establishing a baseline rate of AEs in patients receiving usual care for OIC. The AE profile in the Usual Care arm will be compared with the NKTR-118 arm using descriptive statistics. The risks of participating in the Usual Care arm are expected to be low. Patients assigned to receive Usual Care will be subject to the same monitoring procedures during the study as patients in the NKTR-118 treatment group.

In principle, hypersensitivity reactions, including anaphylactic shock, may occur with the administration of any drug. Consequently, NKTR-118 is contraindicated for any patient with a known hypersensitivity to this product or any other peripheral opioid antagonist, such as methylnaltrexone or alvimopan.

There may be benefits to patients as a result of participating in this study. Randomization to either treatment group may provide symptomatic relief from OIC for the duration of the study. The results of the study may ultimately help in the development of NKTR-118 for treatment of OIC, indirectly benefiting all patients suffering from this condition. There is a great medical need to develop a better and pathophysiologically specific oral medication for the treatment of OIC.

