5.4 Blinding and procedures for unblinding the study

Since this is an open-label study no procedures for blinding or unblinding are applicable.

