5.5.2.2 Usual Care

Patients randomized to the Usual Care treatment arm will follow a laxative treatment regimen for OIC determined by the investigator according to his/her best clinical judgment. For patients randomized to the Usual Care arm, the investigator is advised to treat the patient's OIC as he or she would usually do, following his/her clinical experience, and using laxative agents that are available for treatment of constipation or OIC in their respective country. The investigator may choose from a broad range of laxatives (see Section 5.6.2). However, peripheral μ -opioid antagonists, such as methylnaltrexone and naloxone containing products, are not allowed. The investigator may choose to re-start the laxative that the patient was taking prior to the start of the study if that agent was effective. The investigator will be free to modify the treatment regimen as he/she sees fit throughout the 52-week duration of the trial. No specific rescue laxative protocol is determined for patients randomized to receive Usual Care.

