6.3.2 Definition of adverse events

An AE is the development of an undesirable medical condition or the deterioration/exacerbation of a pre-existing medical condition following or during exposure to a pharmaceutical product, whether or not considered causally related to the product. An undesirable medical condition can be symptoms (eg, nausea, chest pain), signs (eg, tachycardia, enlarged liver), or the abnormal results of an investigation (eg, laboratory findings, ECG). In clinical studies, an AE can include an undesirable medical condition occurring at any time, including run-in or washout periods, even if no study treatment has been administered.

The term AE is used to include both serious and non-serious AEs.

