All AEs spontaneously reported by the patient or reported in response to the open question from the study personnel: “*Have you had any health problems since the previous visit/you were last asked?*,” or revealed by observation will be collected and recorded in the eCRF. When collecting AEs, the recording of diagnoses is preferred (when possible) to recording a list of signs and symptoms. However, if a diagnosis is known and there are other signs or symptoms that are not generally part of the diagnosis, the diagnosis and each sign or symptom will be recorded separately.

Adverse events based on examinations and tests

The results from protocol-mandated laboratory tests and vital signs will be summarized in the CSR. Deterioration as compared to baseline in protocol-mandated laboratory values, and vital signs should therefore only be reported as AEs if they fulfill any of the AE criteria or are the reason for discontinuation of treatment with the IP, or at the discretion of the investigator.

If deterioration in a laboratory value/vital sign is associated with clinical signs and symptoms, the sign or symptom will be reported as an AE and the associated laboratory result/vital sign will be considered as additional information. Wherever possible, the reporting investigator uses the clinical, rather than the laboratory term (eg, anaemia versus low Hb value). In the absence of clinical signs or symptoms, clinically relevant deteriorations in non-mandated parameters should be reported as AE(s).

Deterioration of a laboratory value, which is unequivocally due to disease progression, should not be reported as an AE/SAE.

Any new or aggravated clinically relevant abnormal medical finding at a physical examination as compared with the baseline assessment will be reported as an AE.

Underlying disease progression

Disease progression can be considered as a worsening of a patient’s condition attributable to the disease for which the IP is being studied, which in this study refers to the condition of OIC. Adverse events which are due to disease (ie, OIC) progression, in the opinion of the investigator, should not be reported as an AE, unless they meet SAE criteria (eg, hospitalization, etc., see Section 6.3.3).

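### Non-serious events that the unblinded investigator attributes to OIC progression stay off the AE form, so recorded rates of OIC-like GI events in both arms rest on an arm-aware opinion

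*Protocol*

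**What the plan says.** Under the heading on underlying disease progression, Section 6.3.4 defines progression as a worsening of the condition under study, here OIC, and then rules: "Adverse events which are due to disease (ie, OIC) progression, in the opinion of the investigator, should not be reported as an AE". The sentence goes on with an exception: "unless they meet SAE criteria (eg, hospitalization, etc., see Section 6.3.3". The wording is the same for both arms. No criterion for OIC progression is given beyond worsening of the condition.

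Four other places bear on this rule:

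- Section 5.4: "Since this is an open-label study no procedures for blinding or unblinding are applicable".
- Section 1.4, on the purpose and use of the control arm: "The Usual Care arm is included in this study to allow for establishing a baseline rate of AEs in patients receiving usual care for OIC", and "The AE profile in the Usual Care arm will be compared with the NKTR-118 arm using descriptive statistics". Section 2.2 makes the comparison with Usual Care the secondary objective.
- Section 6.3.2, where the general definition of an AE includes "deterioration/exacerbation of a pre-existing medical condition following or during exposure to a pharmaceutical product".
- Section 5.5.2.2, on Usual Care: "The investigator will be free to modify the treatment regimen as he/she sees fit throughout the 52-week duration of the trial".

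**The concern.** Some symptoms of worsening constipation are also effects of treatment. Section 1.1 says opioid effects on the gut may lead to constipation and other abdominal symptoms, and it lists abdominal pain and nausea among the side effects of constipation treatments. Section 1.4 lists abdominal pain, diarrhea and nausea as the common GI effects of NKTR-118. A non-serious episode of abdominal pain can therefore be read as disease, as a laxative effect or as a drug effect. The first reading keeps it off the AE form; the other two put it on.

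The person choosing the reading knows the arm and, in Usual Care, also chooses and changes the laxatives. Excluding disease progression from AE reporting is a familiar convention when the assessor is blinded. Here it acts at data entry in an open-label trial, on the kind of event most relevant to the comparison for which the Usual Care arm was included. If the two arms are filtered differently, the recorded difference in GI event rates is partly a difference in attribution.

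**Working it through.** **Can the loss be undone from other data?** The protocol's other sources, taken in turn:

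- SAEs are kept by the exception. Severity alone does not keep an event: Section 6.3.4 itself notes that severe nausea need not be an SAE.
- Independent adjudication (Section 6.3.14) names perforation-type and cardiovascular-type events, not ordinary GI events.
- The eDiary is not used during treatment, and the home diary covers medication (Section 3.1).
- The laxative, bisacodyl-accountability and enema eCRFs, the OIC resource-use form (Section 6.9.1) and discontinuation for refractory OIC (Section 5.8) leave traces of worsening. Section 6.9.1 says the resource-use form is not a place to report AEs.

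These allow a partial check on whether OIC worsened more in one arm. None of them returns an event to the non-serious AE tables.

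**Is the rule consistent with the AE definition?** Section 6.3.2 counts deterioration of a pre-existing condition as an AE. Section 6.3.4 removes the non-serious part of exactly that for OIC. Appendix B already handles attribution after recording: deterioration of the studied disease through lack of effect is rated as having no reasonable possibility of a causal link. The exclusion at entry is not needed for that purpose.

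**How large could the effect be?** The protocol gives no figure to reproduce: there is no testing and no formal sample size. The omission shares below are assumptions.

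Inputs: 1135 randomized at 2:1 (Section 3.1). 1135 × 2/3 ≈ 757 on NKTR-118, and 1135 − 757 = 378 on Usual Care.

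Let p be the true proportion of patients with at least one GI event. Let s be the share of those patients whose GI events all go unrecorded; s is defined on patients because Section 12.2.1 counts a patient once per event term. Then

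recorded rate = p × (1 − s)

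recorded difference = p_N(1 − s_N) − p_U(1 − s_U)

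with N for NKTR-118 and U for Usual Care. If p_N = p_U = p, the difference is p × (s_U − s_N), all of it spurious.

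With p = 50% in both arms:

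| s_N | s_U | Recorded N | Recorded U | Difference (points) | Ratio |
|---|---|---|---|---|---|
| 0 | 0 | 50.0% | 50.0% | 0 | 1.00 |
| 10% | 10% | 45.0% | 45.0% | 0 | 1.00 |
| 0 | 10% | 50.0% | 45.0% | +5.0 | 1.11 |
| 0 | 20% | 50.0% | 40.0% | +10.0 | 1.25 |
| 10% | 0 | 45.0% | 50.0% | −5.0 | 0.90 |

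For scale, the 95% half-width of the difference with nothing omitted is 1.96 × √(0.5 × 0.5/757 + 0.5 × 0.5/378) ≈ 6.2 points. A 10-point difference in omission shares produces a bias close to that.

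With unequal true rates, the Phase II figures can serve as a rough guide: "The frequency of any GI AE was 53% in the 25 mg/day dose group and 48% in the corresponding placebo group". The true difference is then 53 − 48 = +5.0 points (ratio 1.10).

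- Equal omission of 10%: 47.7% against 43.2%, difference +4.5, ratio 1.10.
- 10% omitted in Usual Care only: 53.0% against 43.2%, difference +9.8, ratio 1.23.
- 10% omitted in NKTR-118 only: 47.7% against 48.0%, difference −0.3, ratio 0.99.

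The sign of the bias follows whichever arm loses more.

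**The case against.** The strongest defence is that the rule is narrow and even-handed. It covers only worsening of OIC, is worded identically for both arms and keeps everything serious. Section 6.3.4 otherwise requires all reported or observed AEs to be recorded, including new or aggravated clinically relevant examination findings. The primary objective concerns NKTR-118's own safety; the arm comparison is secondary, descriptive and untested. All of this stands, and it limits the point to non-serious events that can be read as OIC. Identical wording does not, however, secure identical application when the arm is known, and a descriptive comparison can mislead just as a tested one can.

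A reader might infer that the Usual Care rate is the one understated. That is plausible: a GI symptom on NKTR-118 has a ready drug explanation, and the causality question asks only about the investigational product. But Section 1.1 gives laxatives the same kinds of GI side effects, so Usual Care symptoms have a treatment explanation too. The protocol does not fix which arm loses more.

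A reader might also infer from the Phase II rates that the gap would double. That needs one-sided omission, and it needs the omitted events to be those patients' only GI events. The rates come from a 4-week placebo comparison, not 52 weeks against laxatives, and include diarrhea, which is hard to call OIC progression. They are not an estimate for this trial.

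**Conclusion.** The point holds for non-serious, OIC-like GI events. Whether such an event reaches the AE tables depends in both arms on an opinion formed with the arm known, under a rule that has no objective criterion and departs from the protocol's own AE definition. Omission can only lower a recorded rate, and only unequal omission biases the ratio. Neither the direction nor the size of the bias follows from the document; a spurious gap of about 5 points for a 10-point difference in omission shares assumes true rates of 50% in both arms. Because the events are never entered, a statistical analysis plan cannot repair this. It is a worthwhile, inexpensive improvement to data collection and does not undermine the primary objective.

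**What to change.** Record these events on the AE form like any other AE, with a yes/no field for whether the investigator attributes the event to OIC progression. Present the AE tables by arm twice, with and without flagged events. The sponsor's convention stays available as one of the two presentations, and the number of flagged events per arm shows whether the judgment was applied differently. Amend the disease-progression paragraph of Section 6.3.4 to match, which also brings it into line with Section 6.3.2.

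The cost is one eCRF field, additional AE records for sites to enter and clean, and one extra set of tables. The AE counts including flagged events will be higher in both arms, and the report should say why.

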6.3.5 Reporting of serious adverse events

All SAEs have to be reported, whether or not considered causally related to the IP, or to the study procedure(s). All SAEs will be recorded in the eCRF.

If any SAE occurs in the course of the study, then investigators or other study site personnel must inform appropriate AstraZeneca representatives within 1 day, ie, immediately, but **no later than the end of the next business day** of when he or she becomes aware of it.

The designated AstraZeneca representative works with the investigator to ensure that all the necessary information is provided to the AstraZeneca Patient Safety data entry site **within 1 calendar day** of initial receipt for fatal and life-threatening events **and within 5 calendar days** of initial receipt for all other SAEs.

For fatal or life-threatening AEs where important or relevant information is missing, active follow-up is undertaken immediately. Investigators or other study site personnel must inform AstraZeneca representatives of any follow-up information on a previously reported SAE within 1 calendar day, ie, immediately, but **no later than the end of the next business day** of when he or she becomes aware of it.

If the eDC system is not available, then the investigator or the other study site personnel reports an SAE to the appropriate AstraZeneca representative by telephone.

The AstraZeneca representative will advise the investigator/study site personnel how to proceed.

Refer to the study-specific Safety Handling Plan for details on SAE reporting using the eDC system.

6.3.6 Daily opioid dose

Opioid doses will be recorded for each patient and the daily opioid dose in morphine equivalents will be calculated. Opioid breakthrough pain medication will be recorded on the relevant eCRF at Visit S1 for new patients (to cover medication taken during the previous 60 days). Information obtained at Visit S1 will be entered into the eDiary to facilitate eDiary recording. Between Visits S1 and R1 opioid breakthrough pain medication will be captured only in the eDiary. At all visits from Visit R1 on, opioid breakthrough pain medication will be recorded on the relevant eCRF for all patients. The daily maintenance opioid dose will be recorded on the relevant eCRF at all visits for all patients. A home diary will be assigned to each patient to facilitate collection of opioid breakthrough pain medication usage.

6.3.7 NRS for pain

Pain intensity is commonly evaluated via single-item measures that require patients to provide a quantifiable categorical and/or numerical rating of their pain. The most evaluated measures of pain intensity include NRS and visual analogue scales; both have been shown to demonstrate excellent psychometric characteristics across a wide range of clinical trial environments. The 11-point NRS has been recommended as the preferred response format for

use in clinical trials ([Dworkin et al 2005](#)). The NRS rates pain from 0 (no pain) to 10 (worst pain imaginable). Changes in this scale should generally not be reported as AEs unless standard criteria for AE reporting are otherwise met.

For new patients, during the OIC confirmation period the NRS will be recorded each evening via the eDiary to record the patients' worst pain and average pain during the day. For all randomized patients, patients will be asked to complete the NRS question on paper form at relevant study visits indicating their average pain during the 7 days prior to the visit. Patients are to fill out the questionnaire in a quiet area, without any help from family, friends, or study staff. With the exception of Visit R1, where some interaction with staff will be necessary in order to ensure that randomization criteria have been met, patients are to fill out the NRS prior to any interventions or discussions regarding their OIC with the study staff or the investigator.

6.3.8 Modified Himmelsbach Scale

Patients are rated by examination for symptoms of opioid withdrawal using the modified Himmelsbach scale. The modified Himmelsbach scale will be administered by a clinician at the study site. Patients will be rated with respect to the following symptoms as observed at the time of the assessment: yawning, lacrimation, rhinorrhea, perspiration, tremor, mydriasis, piloerection, and restlessness. The signs will be quantified on a scale of 0 to 3, with 0=none, 1=mild, 2=moderate, 3=severe. ([Himmelsbach 1941](#); [Culpepper-Morgan et al 1992](#), [Webster et al 2008](#)). To ensure adequate inter-rater agreement, raters will undergo training on proper scoring using the modified Himmelsbach scale and will receive certification provided by Bracket Global. The modified Himmelsbach scale will be administered at screening, randomization, Week 1, Months 1, 3, 6, 9, and 12. Changes in this scale should generally not be reported as AEs unless standard criteria for AE reporting are otherwise met.

6.3.9 Laboratory safety assessment

Laboratory assessments will be conducted at a central laboratory. Blood and urine samples for determination of clinical chemistry, hematology, and U/A will be taken at the times indicated in the Study Plan ([Table 1](#)).

The following clinical laboratory tests (chemistry, hematology, and U/A shown in [Table 2](#)) will be performed as specified in the Study Plan.

Table 2 Laboratory assessments

Hematology	Clinical Chemistry	Urinalysis ^f	Stool Analysis
B-Hb	S-Albumin	U-Glucose	FIT Test ^g
B-Hematocrit	S-ALT ^a	U-Blood	
B-Erythrocyte count	S-ALP	U-Protein	
B-Leukocyte count	S-AST ^a	U-Leukocytes	
B-Leukocyte differential count	S-Bicarbonate	U-Pregnancy test (WOCBP) ^d	
B-Neutrophils (Absolute and %)	S-Bilirubin, Direct ^b	Urine Drug Screen barbiturates benzodiazepines cannabinoids cocaine methadone methaqualone opiates phencyclidine propoxyphene amphetamine tetrahydrocannabinol	
B-Lymphocytes (Absolute and %)	S-Bilirubin, Indirect ^b		
B-Monocytes (Absolute and %)	S-Bilirubin, Total		
B-Eosinophils (Absolute and %)	BUN		
B-Basophils (Absolute and %)	S-Ca		
B-Platelet count	S-Creatinine		
B- MCV	S-Chloride		
B- MCH	S-Glucose		
B- MCHC	S-Potassium		
B- RDW	S-Sodium		
	Total cholesterol ^c		
	TSH		
	S-Pregnancy test ^d		
	Coagulation		
	PT/INR ^e		

ALP alkaline phosphatase, ALT alanine aminotransferase, AST aspartate aminotransferase, B whole blood; BUN blood urea nitrogen, Ca calcium, Hb haemoglobin, INR international normalized ratio, MCH mean corpuscular haemoglobin, MCHC mean corpuscular haemoglobin concentration, MCV mean corpuscular volume, PT prothrombin time, RDW red blood cell distribution width, S serum, TSH Thyroid stimulating hormone, U urine, WOCBP women of childbearing potential.

^a A separate protocol is outlined regarding additional laboratory tests for elevated liver transaminases (see Section 6.3.9.2).

^b Direct and Indirect Bilirubin will be assessed only if the Total Bilirubin value is outside the normal reference range.

^c Total cholesterol will be assessed at randomization, Month 6, and Month 12.

^d Serum pregnancy tests will be performed at Months 1, 3, 6, 9, and the follow-up visit; urine pregnancy tests will be performed at screening (new patients), randomization, and Month 12). Any positive urine pregnancy test is to be followed up with a serum pregnancy test.

^e PT/INR is assessed only at screening for new patients in order to calculate Child-Pugh classification. Screening values from studies D3820C00004 or D3820C00005 will be used for patients who participated in these pivotal studies. INR is also to be assessed during the study if patients meet criteria for significant elevation in liver transaminases (See Section 6.3.9.2)

^f If urinalysis is positive for blood, protein, or glucose, microscopic testing is to be conducted.

^g New patients at average risk for CRC who are ≥50 years old (and who have not had a colonoscopy, barium enema, flexible sigmoidoscopy or virtual colonoscopy) will be asked to take a FIT test as indicated in Appendix E. Patients who enroll from studies D3820C00005 or D3820C00007 will not be required to have additional FIT testing

Serum chemistry and hematology tests will be performed for new patients at Visit S1 (screening), and for all patients at randomization, Week 1, Week 2, Months 1, 3, 6, 9, 12, and at follow-up. Total cholesterol will be assessed at randomization, Month 6, and Month 12.

Urine drug screening tests will be performed for new patients at Visit S1 (screening) and for all patients at randomization, Month 12, and anytime during the study, at the discretion of the investigator, to allow appropriate medical management of the patient. Urinalysis will be performed for new patients at Visit S1 (screening) and for all patients at randomization, Month 6, and Month 12. Urine pregnancy tests (for all WOCBP) will be performed for new patients at Visit S1 (screening) and for all patients at randomization, and Month 12. Any positive urine pregnancy test is to be followed up with a serum pregnancy test. Serum pregnancy tests for WOCBP will be performed at Months 1, 3, 6, 9, and the follow-up visit.

For blood volume, see Section 7.1.

